11.3 ADVERSE EVENTS ASSESSMENT

In the study, all Adverse Events (AEs) will be recorded by Investigator(s), whether the event is considered related to the investigational medical device/procedures or not.

Clinical Investigational Plan			
Protocol No.:	Version 1.0	Page 30 of 45	
01M2020-CH.LMD	Date: 22 December 2020	1 486 30 31 13	

All AEs, regardless of relatedness or outcome, will be reported to Sponsor via the Adverse Event Form of the CRF.

The reporting period for adverse events is from the day the patient performs screening examinations until study exit. Pre-existing conditions (present before the signature of the informed consent) are considered "concurrent medical conditions" and should NOT be recorded as AEs. However, if the subject experiences a worsening or complication of such a concurrent condition, the worsening or complication should be recorded as an AE. Investigators should ensure that the AE term recorded captures the change in the condition (e.g. "worsening of...."). Worsening of pre-existing conditions will be classified as SAE, if matching criteria listed in Section 15.

Investigators will record AE severity and causality. All AEs should be followed to resolution.

The Investigator is responsible for maintaining adequate source documentation relating to AE diagnosis, and treatment. Procedures for investigation and treatment of AEs should be according to site standard of care and Investigator judgment.

Refer to Section 15 for further details.

11.4 ACTIVITIES PERFORMED BY THE SPONSOR REPRESENTATIVE

Activities performed by the Sponsor representative will include:

- training of site staff prior to study start about the desaturation protocol and use of BrOxy M (see Section 13).
- downloading data from the BrOxy M software and the reference software recordings, and data processing (see Section 17).
- monitoring activities (see Section 14)

12 STUDY SUPPLIES/MATERIAL

The following materials will be provided by the Sponsor:

- 3 BrOxy M wearable devices (bracelets)
- One-station charging base (mod. "BrOxy M x1 charging base")
- a cable for USB connection between BrOxy M and PC
- a medical AC / DC converter power supply
- BrOxy M User and installation Manual
- BrOxy M double-sided tape
- 1 Chronograph with timer function
- A PC for the management of measurement acquisitions with BrOxy M software and reference device software installed
- Paper case report forms and study specific binder for archiving of study documents
- Gaseous solutions with 15, 13 and 11% oxygen (rest nitrogen) + medical air

Clinical Investigational Plan			
Protocol No.:	Version 1.0	Page 31 of 45	
01M2020-CH.LMD	Date: 22 December 2020	.0.	

- One way air "HANS RUDOLPH" valve
- 4 Douglas bags (50, 100 or 150 liters)
- Tubing from Gaseous solutions to Douglas bag
- Tubing from Douglas bag to one way air valve
- Disposable mouth filter (Neumofilt Ergo- CE 0051)

All study products will be stored in a safe place and according to package labeling directions, with access limited to study personnel. BrOxy M will be used in accordance with the Instructions for Use (IFU) included in the package and in the study operations binder.

The following materials will be provided by the study site:

- A medical marker or pen to trace references on the subject's skin;
- A flexible tape measure for measuring the circumference of the subject's wrist;
- Reference pulse oximeter.

The equipment provided by the site will be maintained and calibrated according to the site's standard procedures.

12.1 STUDY SUPPLIES/MATERIAL ACCOUNTABILITY

Sponsor delivery of BrOxy M devices and related accessories will be performed in accordance with the site local procedures.

Access to these products should be restricted to study site authorized staff. Use of BrOxy M and the accessories provided by the Sponsor outside of the clinical protocol is strictly prohibited.

The Principal Investigator or Authorized Delegate must keep records documenting the receipt, use, return or disposal of BrOxy M in an appropriate manner and/or in the CRF, as described in the monitoring plan.

12.2 PROCEDURE FOR THE RETURN OF SUSPECTED DEFECTIVE DEVICES

In the event that Investigators and/or Sponsor's representatives suspect the existence of possible defects in the BrOxy M devices or a damaged accessory, such devices shall be returned to Sponsor for further investigation. Investigator or delegate should contact Sponsor for instructions on returning the product.

13 SITE STAFF TRAINING

The study protocol involves procedures which are specific to this study and are not routinely performed during patient care. For this reason, Sponsor expert personnel will provide training to site staff as follows:

• Use of reference device (Nellcor mod.PM1000N) and BrOy M will be reviewed

Clinical Investigational Plan			
Protocol No.:	Version 1.0	Page 32 of 45	
01M2020-CH.LMD	Date: 22 December 2020	Page 32 01 45	

- The desaturation procedure and all associated materials used in the study will be described
- Test simulations will be carried out to create the ventilation circuit (Douglas bag filled with a
 mixture of O₂ and N₂ at a known concentration), the connection system to the inspiratory route
 of the one-way valve, patient connection with filter and fitting to the valve and the bag supply
 system during the test.
- The procedures for replacing the Douglas bag with a mixture of the inspired gas at different O₂ concentration will also be verified.
- Correct data transmission from BrOxy M and the reference device to the PC will be verified
- Instrument synchronization will be checked
- Before starting the study protocol, tests will be carried out to verify compliance with all the
 procedures planned and the delivery times of the gas mixtures as required by the Study
 protocol.

Overall, site staff training, preparation of materials and test simulations, including at least 2 complete tests, will take approximately 4-5 days.

All training will be documented.

In order to ensure that site staff is fully familiar with study procedures, data collected on the first subject will serve to finalize the test set up phase and ensure adequate recording procedures are used by site staff

14 MONITORING AND QUALITY ASSURANCE

Monitoring activities will be performed to ensure that the Investigator and his/her study team conduct the clinical investigation in accordance with the signed Study Agreement, the Study Protocol, any conditions imposed by the Ethics Committee, the Declaration of Helsinki, applicable Good Clinical Practices, and any other applicable regulations, to ensure adequate protection of the rights and safety of subjects and the quality and integrity of the resulting data. The monitor(s) will be qualified by training and experience and possesses the appropriate skills necessary to properly monitor the study.

Due to the ongoing Covid-19 pandemic, monitoring visits may be performed on site or remotely, provided that all necessary systems required to protect data confidentiality are adopted.

In addition to regular monitoring visits, the Sponsor (or designees) may conduct audits at the study site.

15 SAFETY REPORTING

15.1 DEFINITIONS

Adverse Event (AE) (ISO 14155:2020)

Clinical Investigational Plan			
Protocol No.:	Version 1.0	Page 33 of 45	
01M2020-CH.LMD	Date: 22 December 2020	rage 33 01 43	

Untoward medical occurrence, unintended disease or injury, or untoward clinical signs (including abnormal laboratory findings) in subjects, users or other persons, whether or not related to the investigational medical device and whether anticipated or unanticipated

Note 1: This definition includes events related to the investigational medical device or the comparator.

Note 2: This definition includes events related to the procedures involved.

Note 3: For users or other persons, this definition is restricted to events related to the use of investigational medical devices

Serious Adverse Event (SAE) (ISO 14155:2020)

Adverse event that led to any of the following:

- a) death,
- b) serious deterioration in the health of the subject, users, or other persons as defined by one or more of the following:
 - 1) a life-threatening illness or injury, or
 - 2) a permanent impairment of a body structure or a body function including chronic diseases, or
 - 3) in-patient or prolonged hospitalization, or
 - 4) medical or surgical intervention to prevent life-threatening illness or injury, or permanent impairment to a body structure or a body function,
- c) foetal distress, foetal death, a congenital abnormality, or birth defect including physical or mental impairment

Note 1: Planned hospitalization for a pre-existing condition, or a procedure required by the clinical investigation plan, without serious deterioration in health, is not considered a serious adverse event.

Device deficiency (ISO 14155:2020)

Inadequacy of a medical device with respect to its identity, quality, durability, reliability, usability, safety or performance

Note 1: Device deficiencies include malfunctions, use errors, and inadequacy in the information supplied by the manufacturer including labelling.

Note 2: This definition includes device deficiencies related to the investigational medical device or the comparator.

15.2 ANTICIPATED ADVERSE EVENTS

AEs that have been identified as risks through the risk management process and therefore can be considered as "anticipated" for the purposes of this study are:

- temporary slight skin irritation of the wrist related to the use of BrOXy M
- temporary transitory non critical increase of the heart rate and blood pressure
- mild hyperventilation

It is expected that the above symptoms will be resolved in few minutes (<5 minutes) after the interruption/completion of the test session.

Clinical Investigational Plan			
Protocol No.:	Version 1.0	Page 34 of 45	
01M2020-CH.LMD	Date: 22 December 2020	rage 34 01 43	

Refer to Section 8.2 RISKS for further details.

15.3 REPORTING OF ADVERSE EVENTS AND DEVICE DEFICIENCIES

All Adverse Events (AEs) shall be recorded by Investigator(s) on the CRF, whether the event is considered related to the investigational medical device/procedures or not.

Any Serious Adverse Event (SAEs) and device deficiency has to be recorded in the CRF and reported by Investigator to Study Sponsor within 24 hours of having become aware of the event. The Investigator shall also comply with any applicable Ethics Committee requirements for reporting of SAEs.

Study Sponsor has to evaluate any SAE / device deficiency reported from clinical site.

15.4 REPORTING OF INCIDENTS

If an incident is identified or a field safety corrective action is implemented, it shall be reported to the competent authorities concerned according to the applicable regulation for post-market vigilance and per Study Sponsor internal vigilance procedures.

If foreseen by local regulation, any SAE / device deficiency fulfilling the definition of "Incident" shall be reported by the Investigator to the national Competent Authority, according to the procedure in place at the time of occurrence of event.

16 STATISTICAL ANALYSIS

16.1 OVERVIEW

Statistical analyses will be performed with SPSS, Statistical Package for the Social Sciences (SPSS Inc, Chicago, IL), by following the requirements of the standard ISO 80601-2-61:2017 ("Medical electrical equipment - Part 2-61: particular requirements for basic safety and essential performance of pulse oximeter equipment, Procedure for non-invasive laboratory testing on healthy adult volunteers).

The *significance level*, that is the probability of rejecting the null hypothesis when it is true, will be set to 0.05 (two-sided, corresponding 5% risk of concluding that a difference exists when there is no actual difference).

16.2 ANALYSIS SETS

Analyses will regard 320 pair measurements (80 in the ambient air, and 80 for each of the four defined target levels, that will be obtained from 10 healthy subjects).

Clinical Investigational Plan			
Protocol No.:	Version 1.0	Dana 25 of 45	
01M2020-CH.LMD	Date: 22 December 2020	Page 35 of 45	

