8.2 RISKS

Each subject enrolled in the study will be exposed to experimentally generated, controlled hypoxia, starting from $97\% O_2$ and reaching $83\% O_2$ as the lowest level. During the desaturation protocol, which is expected to last a maximum of 35 minutes for each subject, SpO_2 and cardiac frequency will be measured continuously using BrOxy M and the reference device.

The following considerations were made about the potential risks that subjects enrolled in this study will be exposed to:

- Risks associated to the use of BrOxy M and the reference device are negligible, i.e. for BrOxy M a slight irritation of the skin where the bracelet is placed can sometimes be expected. For the reference device subjects may exhibit allergic reactions to the adhesive tape. For this reason subjects with known allergy to adhesive tapes should be excluded from the study
- The absence of pre-existing cardiovascular or pulmonary disease that may expose subjects to increased risks when participating in the study will be carefully checked at screening (see exclusion criteria in Section 10.2)

It is expected that, due to the use of a controlled desaturation protocol foreseen by the standard ISO 80601-2-61:2017, this study is classified as an interventional post-market clinical study in accordance with Annex I of EN ISO 14155:2020.

- Values may be below 90% for a maximum continuous period of 3 minutes. The Principal Investigator will be equipped with a chronograph with a timer and alarm function to avoid exposure of the subjects to longer periods of hypoxia.
- The lowest SpO₂ that subjects will be exposed to is 82% for maximum 3 minutes (30" for stabilization and 2.5' for signal recording). This situation is similar to the one that a subject would have by staying at an altitude of around 3,500-4,000 meters for 3 minutes. Data in literature indicate that there are no risks for healthy subjects for permanence time below 30 minutes at altitudes up to 5,500 m (32).
- The full test will be performed only once on each subject.
- The study will be performed in an outpatient pneumology department, where medical assistance can be promptly provided if necessary.

Clinical Investigational Plan			
Protocol No.:	Version 1.0	Page 23 of 45	
01M2020-CH.LMD	Date: 22 December 2020	.0-	

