16.3.2 Primary endpoint

The **primary endpoint** of the study regards the accuracy of SpO₂ and HR measurements of BrOxy M. The *accuracy* of the experimental BrOxy M will be evaluated by comparing SpO₂ readings of the BrOxy M to the values obtained with the secondary standard pulse oximeter equipment (Nellcor™ Bedside Respiratory Patient Monitoring System model PM1000N, Covidien LLC, USA), that is traceable to co-oximeter SaO₂ values.

The following routines will be used:

- The paired t test, to evaluate the differences between experimental and standard values: the paired sample *t*-test procedure determines whether the mean difference between two sets of observations is zero. It regards *pairs* of observations.
- Correlation analysis, to quantify the degree to which experimental and standard values are related: it is a bivariate analysis that measures the strength of the association between two variables. The degree of association is measured by a correlation coefficient (r) on a scale that varies from + 1 through 0 to 1. We expect a positive correlation: r>0.70 indicate a strong correlation, and r=1 a perfect correlation.
- Concordance correlation coefficient (CCC), to evaluate whether the experimental value is interchangeable with the standard; this statistic quantifies the agreement between a new measurement and a gold standard measurement. Also CCC varies from -1 to 1, with perfect agreement at 1.

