- Bland -Altman (B&A) plot, to evaluate the agreement between experimental and standard values; the B&A plot analysis is a simple way to evaluate a bias between the mean differences, and to estimate an agreement interval, within which 95% of the differences of the second method, compared to the first one, fall. Data can be analyzed both as unit differences plot and as percentage differences. The Bland-Altman chart is a scatterplot with the difference of the two measurements for each sample on the vertical axis and the average of the two measurements on the horizontal axis. Three horizontal reference lines are superimposed on the scatterplot one line at the average difference between the measurements, along with lines to mark the upper and lower control limits of plus and minus 1.96*the standard deviation of the measurement differences. Bland and Altman also discuss the option of using confidence interval bounds, based on the standard error of the mean, for the upper and lower reference lines. If the two methods are comparable, then differences should be small, with the mean of the differences close to 0, and show no systematic variation with the mean of the two measurements. 'Small' would be an amount that would be clinically insignificant for the factor being measured.

Clinical Investigational Plan			
Protocol No.:	Version 1.0	Page 36 of 45	
01M2020-CH.LMD	Date: 22 December 2020		

• Linear regression analysis: to give further information about any potential proportional bias about the mean differences and averages. It is a simple test for a linear trend, with the mean difference as dependent variable and the average difference as independent. The aim is to evaluate if the mean difference can be predicted from the average. The resulting coefficients indicate whether one can accept the null hypothesis that there is no proportional bias.

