17.3 DATA PROCESSING

Subject's data from the paper CRF will be entered manually on an electronic clinical database.

Measurements obtained with the reference device and with BrOxy M will be accessed by the Sponsor Data Manager, and processed as follows. After data acquisition from the devices, first 8 valid paired assessments of SpO_2 and HR will be selected from each plateau as follows:

- Reference device: SpO₂ and HR valid values will be selected starting from at least 30" after plateau stabilization, with a time interval between measurements of at least 20".
- BrOxy M: SpO₂ and HR values generated by BrOxy M will be obtained by processing the
 photoplethysmographic signals generated by the device with the BrOxy Medical software. Then,
 SpO₂ and HR values corresponding to the same time points selected for the reference pulse
 oximeter will be chosen.

As a result, it is expected that up to 32 paired (and synchronized) measurements of SpO₂ and HR will be obtained from each enrolled subject, from the reference device and BrOxy M. Once paired measurements for SpO₂ and cardiac frequency have been obtained at the preselected time points (0, 20", 40", etc.) the list of paired observations will be merged with subject's data in the clinical database.

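### The paired t test in Section 16.3.2 treats up to 320 readings from 10 subjects as separate pairs, so the stated 5% level is not held if a subject's readings are correlated

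*Combined protocol and SAP*

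**What the plan says.** Section 16.2 defines the analysis set by readings: "Analyses will regard 320 pair measurements" "that will be obtained from 10 healthy subjects". Section 10 describes 320 as a maximum, at 32 pairs per subject. Section 8.2 adds: "The full test will be performed only once on each subject". All of a subject's pairs therefore come from one session. Section 17.3 takes the "first 8 valid paired assessments" from each plateau, with at least 20 s between readings.

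Section 16.3.2 lists five routines for the primary endpoint without ranking them: paired t test, correlation, concordance correlation coefficient (CCC), Bland-Altman plot, and a regression for proportional bias. Of the t test it says that the "procedure determines whether the mean difference between two sets of observations is zero". Section 16.1 sets a two-sided level of 0.05, glossed as a "corresponding 5% risk of concluding that a difference exists when there is no actual difference".

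The Bland-Altman lines are set at "plus and minus 1.96*the standard deviation of the measurement differences". The plan also notes that the method's authors "discuss the option of using confidence interval bounds, based on the standard error of the mean", but does not commit to doing so.

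No section mentions a subject effect, clustering, per-subject averaging or a mixed model.

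**The concern.** A t test on 320 differences has a 5% error rate only if the 320 differences are independent. Here up to 32 of them share a person, a wrist and a session. The plan itself treats skin pigmentation, a property of the subject, as a possible influence on accuracy (Sections 7.2 and 16.3.3). Such an influence would give all of a subject's differences a common component. With 10 people, the average difference then depends heavily on which 10 were recruited, and a standard error built on 320 pairs does not see this.

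At stake is how the SpO2 and HR bias is read. A significant result may reflect only the chance make-up of the group, and that error counts against the device. In other settings the test is too cautious and could miss a real bias. The proportional-bias regression tests a null hypothesis on the same pairs. P-values or intervals for the correlation and the CCC would share the fault.

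**Working it through.** **Inputs.** 10 subjects (Section 16.2); 4 plateaus with 8 readings each (Table 1); two-sided level 0.05 (Section 16.1). The ICC of the paired differences is assumed, because the documents give none.

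**The plan's count.** 10 × 4 × 8 = 320, which reproduces Section 16.2. Read literally, that section's breakdown (80 in ambient air plus 80 at each of four levels) gives 400, but Table 1 counts ambient air as one of the four plateaus.

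**Error rate by formula.** With m readings per correlated group, the variance of the overall mean is multiplied by DE = 1 + (m − 1) × ICC. The actual error rate is then about 2 × [1 − Φ(1.96/√DE)].

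- Correlation across the session, m = 32, ICC 0.1: DE = 1 + 31 × 0.1 = 4.1; 1.96/√4.1 = 0.968; error about 33%. The 320 pairs carry the information of about 320/4.1 = 78.
- Correlation within a plateau only, m = 8, ICC 0.1: DE = 1 + 7 × 0.1 = 1.7; error about 13%.
- Plateau offsets of +1 and −1 SD in alternation cancel in the mean but raise the pooled variance from 1 to about 2. The formula becomes 2 × [1 − Φ(1.96 × √2/√DE)]. At ICC 0.1 across the session: 1.96 × 1.414/2.025 = 1.37; error about 17%.

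**Error rate by simulation.** 20,000 runs per setting, normal differences with random variance 1, true overall bias zero. Rejection rate of the 5% t test on 320 pairs:

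| Assumed ICC | Session-wide, no offsets | Plateau-only, no offsets | Session-wide, 1 SD offsets | Plateau-only, 1 SD offsets |
|---|---|---|---|---|
| 0.01 | 9% | 6% | 1.6% | 1% |
| 0.05 | 22% | 9% | 8.5% | 2% |
| 0.1 | 33% | 13% | 17% | 3% |
| 0.3 | 55% | 27% | 39% | 12% |
| 0.5 | 64% | 36% | 50% | 19% |

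A t test on the 10 subject means (9 df, critical value 2.262) rejects in about 5% of runs under session-wide correlation with equal counts, with or without the offsets.

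**Interval for the bias.** Session-wide correlation, no offsets, ICC 0.05 / 0.1 / 0.3 / 0.5. The naive 95% half-width is 0.110 / 0.109 / 0.108 / 0.106 SD; with the subject as unit it is 0.196 / 0.249 / 0.395 / 0.499 SD. The ratios are about 1.8 / 2.3 / 3.7 / 4.7. With 1 SD offsets they fall to 1.3 / 1.6 / 2.6 / 3.3, and at ICC 0.01 to 0.9, where the naive interval is slightly too wide.

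**Bland-Altman lines.** At ICC 0.5 the pooled SD averages 0.968 of the true SD, a shift of about 3%. In a single study, however, its central 95% range is about 0.78 to 1.22 times the true SD.

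**Unequal counts.** With an assumed loss leaving about 237 pairs on average, session-wide correlation and no offsets, the naive test rejects in 7 / 18 / 29 / 50 / 58% at the five ICCs. Over the unequal-count settings run, a mixed model with fixed plateau, random subject and 9 df rejects in 2.2 to 5.1%.

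**The case against.** The t test is one of five unranked routines, and no pass or fail decision hangs on it. A reader might infer that the device could be wrongly failed on this p-value. The documents do not support that: they set no acceptance rule on it.

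The size of the error is assumed throughout. The gas mixture and saturation change between plateaus, so correlation might be confined to a plateau; from ICC 0.05 upward, without offsets, that gives little more than half the session-wide rates or less. A reader might also infer that the test is always too liberal, or that a naive interval is always too narrow. Neither is general: with 1 SD offsets and plateau-only correlation at ICC 0.05, the rejection rate is about 2%. These points limit the claim, but they do not restore the 5% level.

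Section 16.1 says the analysis follows ISO 80601-2-61:2017, which might contain an adjustment. The documents do not say that it does, and the listed routines include none. The supportable statement is that no allowance for repeated readings is stated, not that the standard is breached.

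Finally, the 1.96 SD lines hardly move on average. That stands, but only as an average; their uncertainty still depends on having 10 subjects.

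**Conclusion.** The plan is wrong as written on this point and should be fixed before analysis. It claims a two-sided 5% level for a test that holds it only if all pairs are independent. Without plateau bias, the actual rate runs from about 6% to 64% over ICC 0.01 to 0.5 and the two correlation patterns. With cancelling 1 SD plateau biases it runs from about 1% to 50%. These figures rest on assumed ICCs, equal correlation within each group, normal differences and complete data.

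The consequence is a p-value, and any interval for the bias, that misstates the precision 10 subjects can give. It does not follow that the study's conclusion would be reversed, or that the planned limits of agreement are badly biased.

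**What to change.** In Section 16.3.2:

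- Test and estimate the mean SpO2 and HR difference by a t test and 95% CI on the subject means.
- If valid counts differ between subjects, use a mixed model on the differences with fixed plateau, random subject and subject-level degrees of freedom, and note that it can be conservative at low ICC. Unequal counts are likely: eight readings 20 s apart span 7 × 20 = 140 s, which leaves little slack in a 150 s plateau. If the time points are fixed in advance, as Section 17.3 also suggests, any rejected window over a time point loses a reading.
- Give the proportional-bias regression the same unit, for example one slope per subject, or a random subject intercept and slope.
- Take any CI or p-value for the correlation, CCC and limits of agreement from a method that treats the subject as the unit. Do not use lines based on the standard error of the mean as limits of agreement.
- State that a non-significant difference is not evidence of agreement.

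The cost is SAP wording and a little more analysis, with no new data and no change to the session. Under session-wide correlation without plateau bias, the bias interval becomes about 1.8 / 2.3 / 3.7 / 4.7 times the naive width at ICC 0.05 / 0.1 / 0.3 / 0.5. With the SD of a subject mean taken as √(ICC + (1 − ICC)/32), power to detect a bias of 0.3 SD with 10 subjects is 85 / 66 / 32 / 22%. With 12 subjects it is 92 / 75 / 39 / 26%.
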